- **Exposed during pregnancy by trimesters** – *in utero* exposed to anifrolumab will be determined for each pregnancy trimester (dichotomous variables) and combined into a pattern of exposure by trimester (Table 6). The exposure by trimester will be defined as:
 - in each trimester, offspring whose mother had at least one prescription/dispensations/administration of anifrolumab leading to an exposure period overlapping with a specific trimester(s), will be classified as exposed (yes/no) (Table 6);
 - offspring whose mother had no anifrolumab prescription/dispensations/administration in the 16 weeks (anifrolumab window of clearance) prior to LMP2 or during all pregnancy, with the assumption of continuing treatment with SOC, will be classified as non-exposed (yes/no) (Table 6).

Table 6: Maternal exposure status by trimester, offspring *in utero* exposed to anifrolumab (polytherapy) vs offspring *in utero* exposed to SLE SOC

Exposed group				Comparator group		
1 st trimester	2 nd trimester	3 rd trimester		1 st trimester	2 nd trimester	3 rd trimester
anifrolumab (+ SOC)	SOC ¹	SOC ¹	VS	SOC	SOC ¹	SOC ¹
anifrolumab (+ SOC)	anifrolumab (+ SOC)	SOC ¹	VS	SOC	SOC	SOC ¹
anifrolumab (+ SOC)	anifrolumab (+ SOC)	anifrolumab (+ SOC)	VS	SOC	SOC	SOC
SOC	anifrolumab (+ SOC)	anifrolumab (+ SOC)	VS	SOC	SOC	SOC
SOC	SOC	anifrolumab (+ SOC)	VS	SOC	SOC	SOC

Abbreviations used in the table: SOC, Standard of care; VS, Versus

¹ SOC might not be applicable if pregnancy ends early

Definition of exposure period

Women exposed to anifrolumab during pregnancy are included in the exposed groups regardless of the exposure status before pregnancy. The maximum exposure period is from LMP2 to delivery/birth. The maternal exposure period during pregnancy is not considered to be fixed. This is because pregnancy duration is not exactly the same for all pregnancies (full-term birth is considered between 37 to 42 weeks of gestation). Also, exposure period can end earlier with a censoring event (e.g., elective termination of pregnancy).

The definition of exposure period relies on available information on the date of prescription/dispensation/administration, the expected supply (i.e., package size, the number of packages prescribed/dispensed), and the estimated window of drug clearance (for anifrolumab, the time for concentration to fall below the LLOQ for 95% of patients is 16 weeks from last administration). The exposure period starts on the date when the drug was administered or

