MCM (defined as a composite of all major MCMs) among live and non-live offspring: The first primary outcome of interest is MCM occurring in live or non-live offspring. MCM is defined as defects of prenatal origin that have either cosmetic or functional significance to the child's health, development, or survival. MCM ascertainment will be based on the presence of an ICD-10 code (or other database specific coding system [codes to be adapted to the coding systems used in each of the data sources]) in the database. These ICD-10 codes will be classified according to the EUROCAT (Description of the Congenital Anomaly Subgroups in EUROCAT Guide 1.5) classification scheme, as four of the five data sources are in Europe (41). As there are some differences in the classification of MCMs by different classification schemes, the USA CDC definition of MCM as an abnormality of body structure or function that is present at birth, is of prenatal origin (i.e., birth defect), has significant medical, social, or cosmetic consequences for the affected individual, and typically requires medical intervention as implemented by the Metropolitan Atlanta Congenital Defects Program (MACDP) will also be implemented as a sensitivity analysis (see Section 9.7.5) (15, 24). The list of the MCM and their respective ICD-10 codes are presented in Table 22a using the EUROCAT classification. The MACDP 6-digit code defect list for major congenital malformations is presented in Table 22b.

The MCM ascertainment period is defined as:

- for live births, from birth until 1 year of age
- for non-live births (spontaneous abortion and stillbirth) an ICD-10 of MCM as the diagnosis at end of pregnancy
- for elective terminations, an ICD-10 code of an MCM as the reason for the termination at termination of pregnancy.

Select pregnancy loss outcomes (composite of spontaneous abortion and stillbirth) among all pregnancies

The second primary outcome of interest is select pregnancy loss outcomes, a composite of spontaneous abortion and stillbirth (Table 24).

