For the select pregnancy loss outcomes, the **index date/start of follow-up**, will be defined as the LMP2 (as defined in Section 9.1) from which the pregnancy will be followed until the outcome of interest. The **exit date/end of follow-up**¹¹ will be defined as the end of the study period, death, emigration (where available), loss to follow-up (disenrollment/de-registering), or date of first diagnosis of the outcome at study, or delivery, whichever is the earliest.

The select pregnancy loss outcomes will be defined as the presence of at least one of the following criteria:

- ICD-10 code of spontaneous abortion¹² (unintended loss of an intrauterine pregnancy) which is less than 22 weeks of gestation for the European data sources (40); less than 20 weeks for the USA data sources (64);
- ICD-10 code of stillbirth¹³ (unintended foetal death occurring at or after 22 weeks of gestation for the European data sources (78); at or after 20 weeks for the USA data sources (64).

Secondary outcomes

During the outcome ascertainment period, outcome events will be identified based on ICD-10 CM codes for the USA, ICD-10 for Denmark, Finland and France; MedDRA codes for Germany recorded in patient registries.

Minor congenital malformations

For this outcome the **index date/start of follow-up**, will be defined as the LMP2 (as defined in Section 9.1) from which the foetus/offspring will be followed up for the outcome of interest. The **exit date/end of follow-up** will be defined as the end of the study period, death, emigration (where available), loss to follow-up (disenrollment/de-registering), reaching the age of 1 year or date of first diagnosis of the outcome at study, whichever is the soonest.

¹¹ Specific outcome censoring rules will be applied. For spontaneous abortion outcome specific end of follow-up will be 22 weeks of gestation for the European data sources or 20 weeks for the USA data sources further details will be specified in the SAP.

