- **Proportion of unexposed to confirmed teratogenic SLE SOC and/or non-SLE SOC drugs of 80%.** It is estimated that 80% of the SLE pregnancies are not exposed to SLE SOC and non-SLE SOC confirmed teratogenic drugs before conception, with a time period of 5-half-lives of relevant drug (see list of confirmed teratogenic drugs and half-lives in Table 20), or during pregnancy. This estimate is based on the reported use of SLE SOC and/or non-SLE SOC drugs in SLE population (47, 48).
- **Proportion of anifrolumab exposure during the first trimester of pregnancy of 80%.** The majority of the anifrolumab exposed pregnancies are expected to be unplanned and exposed to anifrolumab only in the early stages of the pregnancy, as the current recommendations indicate that anifrolumab should only be used during pregnancy if the benefit outweighs the risk to the foetus (86). We therefore used the assumption that 80% of all anifrolumab exposed pregnancies are exposed to anifrolumab during the first trimester of pregnancy.
- **Proportion of anifrolumab exposed pregnancies in women with moderate-to-severe SLE of 5% and 10%.** Based on market forecasts, uptake of anifrolumab in the general SLE population is expected to grow from 5% within two years of market launch to 20% by 5 years after market launch. Given the uncertainty of how these forecasts apply to SLE women of child-bearing potential and to use in pregnant SLE women, we used a conservative lower bound (5%) and a more realistic midpoint value (10%) for the proportion of pregnancies in women with moderate-to-severe SLE exposed to anifrolumab.

In addition, to estimate the minimum required sample size and the expected power, the following assumptions were used:

- **Non-inferiority margin of RR of 2.5.** The RR of 2.5 was based on previously reported increase in risk of MCM for exposure to a major teratogenic drug (62).

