In the descriptive analysis, the total number of patients at risk and the number of events for each study outcome in the study sub-cohorts (exposed to anifrolumab and unexposed to anifrolumab as defined in Section 9.2.2) will be tabulated before and after application of PS adjustment, if suitable for the data. The measures of study outcomes will be estimated before and after application of PS adjustment (if suitable for the data) to obtain crude and adjusted estimates, respectively. The measures of study outcomes, with associated 95% CIs, will be estimated for the study sub-cohorts exposed to anifrolumab and unexposed to anifrolumab as defined in Section 9.2.2. In this study, cumulative incidence (i.e. incidence proportion) by exposure status to anifrolumab during pregnancy will be assessed for the following study outcomes: MCM (objective 1 & 15), select pregnancy loss outcomes (composite of spontaneous abortion and stillbirth) (objective 3 & 13), mCM (objective 6), adverse pregnancy outcomes (objective 8), adverse birth outcomes (objective 10), and adverse outcome related to infant growth up to one year of age (objective 12).

Additionally, the description of the time from birth to MCM ascertainment will be conducted in live and non-live offspring from women who had moderate/severe SLE and were exposed or unexposed to anifrolumab during the first trimester of pregnancy. The time to MCM ascertainment will be calculated from birth and up to 1 year after birth. The time to MCM ascertainment will be estimated both before and after application of PS adjustment (if suitable for the data) to obtain crude and adjusted estimates, respectively. Kaplan-Meier curves (and their 95% CIs) will be used for characterising the time from birth to MCM ascertainment. Together with the Kaplan-Meier curves, the number of patients at risk at appropriate time intervals (e.g., 7 days or as seen appropriate for the study), and the median (with 95% CI) for the time from birth to MCM ascertainment will be reported.

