For the comparison of the study sub-cohorts exposed to anifrolumab and unexposed to anifrolumab within the study cohorts (as defined in Section 9.2.2), the association metrics of RRs will be estimated. The RRs will be estimated if there is at least one outcome event observed per exposure group. Both crude and adjusted RRs will be reported and estimated for each relevant study outcome. The crude and adjusted RRs will be estimated before and after PS adjustment, respectively. The adjusted RRs will be reported only if PS adjustment is suitable for the data. The statistical model to be used for the estimation of the crude and adjusted RRs will be the log-binomial regression or the robust, modified Poisson regression as seen appropriate for the study data (13, 18). If covariate balance is not achieved through PS adjustment, additional adjustment by using unbalanced covariates in the outcome regression model will be considered. Additionally, any other potential covariates (or risk factors) that are not included in the PS model but are hypothesised to be associated with the study outcomes may be used as covariates for the statistical models. Further details on the statistical models will be provided in the SAP.

Meta-analysis

In addition to data source level analyses, results will be combined in a meta-analysis. Meta-analysis will be performed only for the adjusted RR estimates of the primary study objectives (MCM and selected pregnancy loss outcomes). The meta-analysis will be performed using effect size estimates from all study countries for which the adjusted RR were estimated.

Prior to conducting the meta-analyses, heterogeneity across the study countries will be assessed using:

- Cochran's Q test (significance level: 0.1). Q is calculated as the weighted sum of squared differences between individual studies and the pooled value across studies.
- The I^2 statistic (0% to 40%: might not be important; 30% to 60%: may represent moderate heterogeneity; 50% to 90%: may represent substantial heterogeneity; 75% to 100%: considerable heterogeneity). I^2 is calculated as follows:

$$I^2 = \left(\frac{Q - df}{Q} \right) \times 100\%$$

where Q is Cochran's statistic and 'df' is its degrees of freedom. The I^2 is a statistic that estimates the percentage of variance in effects attributable to study heterogeneity rather than sampling error.

- The τ^2 statistic

Considerable heterogeneity would indicate that the study results should be interpreted as inconclusive.

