as described in Section 9.7.1. In addition, meta-analysis on the data source specific crude and adjusted RRs of MCM in live and non-live offspring from mothers who were exposed or unexposed to anifrolumab during pregnancy will be conducted as described in Section 9.7.1.

Objective 3

The analysis to describe and estimate the risk of select pregnancy loss outcomes (composite of spontaneous abortion and stillbirth) in all pregnancies from the mothers who had moderate/severe SLE and were exposed or unexposed to anifrolumab during pregnancy (study objective 3) will be performed using the *pregnancy* cohort (as defined in Section 9.2.2). The crude and adjusted cumulative incidence (with corresponding 95% CI) of the select pregnancy loss outcomes (composite of spontaneous abortion and stillbirth) will be estimated for cases where mother was exposed to anifrolumab during pregnancy and for cases where mother was unexposed to anifrolumab during pregnancy. The crude cumulative incidence (i.e., risk) will be calculated as the total number of select pregnancy loss outcomes (composite of spontaneous abortion and stillbirth) divided by the total number of pregnancies. The adjusted cumulative incidence (i.e., risk) will be estimated following PS adjustment, if suitable for the data.

Objective 4

To estimate the relative risk of select pregnancy loss outcomes (composite of spontaneous abortion and stillbirth) in pregnancies from the mothers who had moderate/severe SLE and were exposed or unexposed to anifrolumab during pregnancy (study objective 4), the crude and adjusted RR (with corresponding 95% CI) will be estimated using the *pregnancy* cohort (as defined in Section 9.2.2). The crude RR and its 95% CI will be estimated using a regression model as specified in Section 9.7.1. The adjusted RR and its 95% CI will be estimated using the same regression model following an appropriate PS adjustment method as described in Section 9.7.1.

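### The primary pregnancy-loss risk keeps elective terminations in the denominator as non-events, so an excess of terminations among exposed pregnancies would bias the RR downward, and no planned analysis tests for this

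*Protocol*

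**What the plan says.** - **Outcome (9.3.2).** "The second primary outcome of interest is select pregnancy loss outcomes, a composite of spontaneous abortion and stillbirth". Elective termination is not a component.
- **Risk (9.7.2, Objective 3).** The crude risk is the "total number of select pregnancy loss outcomes (composite of spontaneous abortion and stillbirth) divided by the total number of pregnancies". Section 9.7.1 calls the measure "cumulative incidence (i.e. incidence proportion) by exposure status to anifrolumab during pregnancy will be assessed for the following study outcomes".
- **RR (9.7.1).** The model is "the log-binomial regression or the robust, modified Poisson regression as seen appropriate for the study data". Neither option uses gestational time.
- **Cohort (9.2.2, Table 5).** Ectopic pregnancies are taken out of the pregnancy cohort for this outcome. Elective terminations are not.
- **End of follow-up.** For select pregnancy loss, the exit list in 9.3.2 closes with "or date of first diagnosis of the outcome at study, or delivery, whichever is the earliest" and does not name elective termination. Note i to Figure 2 (9.1), the design schema for this outcome, does end follow-up there. Section 9.3.1 says the "exposure period can end earlier with a censoring event (e.g., elective termination of pregnancy", but this concerns exposure, not the outcome.
- **Exposed pregnancies (9.5.1.1).** "The majority of the anifrolumab exposed pregnancies are expected to be unplanned and exposed to anifrolumab only in the early stages".
- **Elsewhere.** Table 7 lists no covariate for pregnancy intention. Neither the sensitivity analyses (9.7.5) nor the limitations (9.9) treat termination as precluding loss. Elective termination is a secondary outcome with its own RR, and it is part of the secondary foetal-loss composite (9.3.2; 9.7.3, Objectives 8 and 9).

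**The concern.** A pregnancy terminated at 8 weeks can no longer end in spontaneous abortion or stillbirth. In a simple proportion it adds one to the denominator and nothing to the numerator. If both groups terminate equally often and at similar times, this cancels in the ratio. If the exposed terminate more often, for example because the pregnancy was unplanned, their observed loss risk falls for a reason unrelated to foetal toxicity. The propensity score cannot directly correct this, because intention is not among its candidate variables.

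This endpoint follows up the embryo-foetal loss finding in monkeys (7.4 and 7.5) and is sized to rule out an RR of 2.5. An RR that is too low makes that easier. Harmonising exit dates alone would not help, because an exit date has no effect on a proportion of all pregnancies.

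**Working it through.** **The plan's own figures first.** Inputs from 9.5: loss risk 20%, margin 2.5, one-sided 2.5%, power 80%. With Poisson variance,

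n(exposed) = (1.96 + 0.84)² × (1/0.20) × (1 + 1/ratio) / ln(2.5)².

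This gives 71 at 1:2 (stated 72) and 63 at 1:3 (stated 61). Simulating the Protocol's scheme gives 81.9% power at 72 and 79.3% at 61. Power exceeds 99% at the expected numbers, as stated. The sample size is not in error.

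**Bias factor.** Let e1 and e0 be the shares of ongoing exposed and comparator pregnancies that are terminated. Let f be the fraction of the loss risk still ahead at termination, the same in both groups. Losses in a group fall from L to L(1 − f·e), so

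observed RR / RR without terminations = (1 − f·e1) / (1 − f·e0).

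The Protocol gives none of e1, e0 or f; all are assumptions. The last column is the simulated chance that the upper 95% limit falls below 2.5 when the true RR is 2.5 (risks 0.50 v 0.20, 1:2). It uses 481 exposed (163 + 162 + 11 + 145, the four sources pooled at 10% uptake), first with a Poisson standard error and then with a binomial-type one.

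| e1 v e0 | f | Factor | True 2.5 reads as | False rule-out |
|---|---|---|---|---|
| 5% v 5% | 1 | 1.000 | 2.50 | 0.9% / 2.6% |
| 10% v 5% | 1 | 0.90/0.95 = 0.947 | 2.37 | 4.4% / 9.9% |
| 20% v 10% | 1 | 0.80/0.90 = 0.889 | 2.22 | 16% / 27% |
| 20% v 5% | 1 | 0.80/0.95 = 0.842 | 2.11 | 36% / 51% |
| 20% v 5% | 0.5 | 0.90/0.975 = 0.923 | 2.31 | 8% / 17% |
| 5% v 10% | 1 | 0.95/0.90 = 1.056 | 2.64 | 0.1% / 0.5% |

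More data do not help. For 20% v 5% with f = 1, false rule-out is 5% / 11% at 72 exposed, 17% / 29% at 236 (5% uptake) and 36% / 51% at 481, because the interval tightens around a biased value.

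**Would dropping terminations from the denominator solve it?** Only if they all precede losses: 0.842 × 0.95/0.80 = 1.00. With f = 0.5 it overcorrects. Removing the full shares gives 0.923 × 0.95/0.80 = 1.10. Removing only pregnancies still ongoing after a loss risk of 0.10 gives 0.923 × (1 − 0.05 × 0.90)/(1 − 0.20 × 0.90) = 0.923 × 0.955/0.82 = 1.08. Exclusion is therefore a bound, not a replacement.

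**The case against.** **The proportion is a legitimate quantity.** The share of all pregnancies ending in spontaneous loss, with terminations occurring as they do, is a valid cumulative incidence in the presence of a competing event. The risk had nobody terminated is a different, hypothetical quantity that needs an assumption about why women terminate. This stands, and it is why the primary estimate need not be replaced. It does not make an RR shifted by differing termination rates safe to read as evidence on foetal toxicity.

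**The direction is not established.** A reader might infer that the planned RR will be biased downward. The documents do not support that: they give no termination rates and do not say that comparator pregnancies are planned. Comparators' use of standard of care does not separate the groups, since the exposed take it too. With equal shares there is no bias, and with fewer terminations among the exposed it reverses.

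**Follow-up may already end at termination.** A reader might infer from the 9.3.2 exit list that termination is ignored. Note i to Figure 2 names it, Table 3 follows the mother to the end of pregnancy, and footnote 11 leaves outcome-specific censoring rules to the SAP. The exit-rule point is therefore one of reconciliation. The estimator, however, is already fixed in 9.7.2.

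**An imbalance would be visible.** Elective termination has its own adjusted RR. That would reveal an imbalance but would not correct the primary RR or say what to conclude from it.

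**Conclusion.** The point holds as a gap in the primary pregnancy-loss analysis: terminations stay in the denominator as non-events, and nothing planned shows how far that moves the RR. Under the assumed shares, the factor runs from 0.84 (20% v 5%, all terminations before losses) through 1.00 (equal shares) to 1.06 (5% v 10%). It is 0.95 for a modest excess of 10% v 5%.

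A reader might infer that a drug that raises miscarriage could look neutral. That holds only for modest true effects. The true RR that would read as 1.0 is 1/0.947 = 1.06 at 10% v 5% and 1/0.842 = 1.19 at 20% v 5%. Even at an assumed 40% v 10% it is 0.90/0.60 = 1.50. A true 2.5 still reads as 2.11 at 20% v 5%. What is exposed is the conclusion that 2.5 has been ruled out, because that depends on the upper confidence limit.

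**What to change.** 1. Keep the all-pregnancies proportion as the primary estimate for Objectives 3 and 4.
2. Reconcile the 9.3.2 exit rule for select pregnancy loss with note i to Figure 2, so that elective termination ends follow-up in both.
3. Add to 9.7.5 a pre-specified sensitivity analysis of the select-loss RR on the gestational-age scale, censoring at elective termination and keeping live birth as a competing event.
4. Add a bounding analysis that removes from the denominator terminations not made for foetal anomaly. Section 9.3.2 already captures the reason where possible. State that this can overcorrect, by about 1.08 to 1.10 in the example above.
5. Report termination frequency by exposure group beside the primary RR, and make the conclusion that an RR of 2.5 is ruled out conditional on agreement across these analyses. Add the issue to 9.9.

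**Cost.** Protocol wording and two extra analyses, with no new data collection. The gestational-time analysis assumes termination is non-informative given covariates, which is doubtful where it follows a foetal anomaly or maternal illness. Intervals will be slightly wider. Event timing is the main weakness: 9.3.3 says gestational age is rarely available for miscarriages, and the Carelon algorithm (Appendix C, Table 17, note 2) assigns a fixed value when no codes exist. Many event times would be imputed, which is a further reason to make this analysis supportive rather than primary.

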9.7.3 Secondary objectives

The analysis for the secondary study objectives will be conducted separately for each data source. The description of the analysis to be conducted for each secondary study objective is provided in the following sections.

Objective 5

To describe the demographic and clinical characteristics of the live and non-live offspring and their mothers who had moderate/severe SLE and were exposed or unexposed to anifrolumab during the first trimester of pregnancy or anytime during pregnancy (study objective 5), the descriptive analysis of the demographic and clinical characteristics (as defined in Section 9.3.3) will be provided as described Section 9.7.1. The demographic and clinical characteristics of the

live and non-live offspring and their mothers will be presented separately for each study cohort and sub-cohorts as defined in [Table 5](#) (Section [9.2.2](#)). No statistical testing comparing the distribution of demographic and clinical characteristics distribution between the study cohorts or sub-cohorts is planned.

Objective 6

The analysis to describe and estimate the risk of mCM in live and non-live offspring from the mothers with moderate/severe SLE who were exposed or unexposed to anifrolumab during pregnancy (study objective 6) will be performed using the *mCM* cohort and its sub-cohorts as defined in Section [9.2.2](#). The crude and adjusted cumulative incidence (with corresponding 95% CI) of the mCM in live and non-live offspring from the mothers will be estimated separately for the case where mother had moderate/severe SLE and was exposed or unexposed to anifrolumab during pregnancy. The crude cumulative incidence (i.e., risk) will be calculated as the total number of live and non-live offspring with mCM divided by the total number of live and non-live offspring. The adjusted cumulative incidence (i.e., risk) will be estimated following PS adjustment described in Section [9.7.1](#).

Objective 7

To estimate the relative risk of mCM in live and non-live offspring from the mothers who had moderate/severe SLE and were exposed or unexposed to anifrolumab during pregnancy (study objective 7), the crude and adjusted RRs (with corresponding 95% CI) will be estimated using the *mCM* cohort. The crude RR and its 95% CI will be estimated using a regression model as specified in Section [9.7.1](#). The adjusted RR and its 95% CI will be estimated using the same regression model following an appropriate PS adjustment method as described in Section [9.7.1](#).

Objective 8

The analysis to describe and estimate the risk of adverse pregnancy outcomes (as defined in Section [9.3.2](#)) in all pregnancies from the mothers who had moderate/severe SLE and were exposed or unexposed to anifrolumab during pregnancy (study objective 8) will be performed using the *pregnancy* cohort (as defined in Section [9.2.2](#)). The crude and adjusted cumulative incidence (with corresponding 95% CI) of the adverse pregnancy outcomes (as defined in Section [9.3.2](#)) will be calculated for cases where the mother was exposed to anifrolumab during pregnancy and for cases where the mother was unexposed to anifrolumab during pregnancy. The crude cumulative incidence (i.e., risk) will be calculated as the total number of each adverse pregnancy outcome (as defined in Section [9.3.2](#)) divided by the total number of pregnancies. The adjusted cumulative incidence (i.e., risk) will be estimated following PS adjustment.

Objective 9

To estimate the relative risk of adverse pregnancy outcomes (as defined in Section 9.3.2) in pregnancies from the mothers who had moderate/severe SLE and were exposed or unexposed to anifrolumab during pregnancy (study objective 9), the crude and adjusted RR (with corresponding 95% CI) will be estimated using the *pregnancy* cohort (as defined in Section 9.2.2). The crude RR and its 95% CI will be estimated using a regression model as specified in Section 9.7.1. The adjusted RR and its 95% CI will be estimated using the same regression model following an appropriate PS adjustment method as described in Section 9.7.1.

Objective 10

The analysis to describe and estimate the risk of adverse birth outcomes in live offspring from the mothers who had moderate/severe SLE and were exposed or unexposed to anifrolumab during pregnancy (study objective 10) will be performed using the *birth* cohort (as defined in Section 9.2.2). The crude and adjusted cumulative incidence (i.e., risk) for the adverse birth outcomes will be calculated for cases where mother was exposed to anifrolumab during pregnancy and for cases where mother was unexposed to anifrolumab during pregnancy. The crude cumulative incidence (i.e., risk) will be calculated as the total number of each adverse birth outcome divided by the total number of live offspring. The adjusted cumulative incidence (i.e., risk) will be estimated following PS adjustment.

Objective 11

To estimate the relative risk of adverse birth outcomes in live offspring from the mothers who had moderate/severe SLE and were exposed or unexposed to anifrolumab during pregnancy (study objective 11), the crude and adjusted RRs (with corresponding 95% CI) will be estimated using the *birth* cohort (as defined in Section 9.2.2). The crude RR will be estimated using a regression model. The adjusted RR will be estimated following PS adjustment, if suitable for the data, and using a regression model.

